6.5.5 Pollen count

Pollen counts will be quantitated retrospectively for the purposes of analysis. *Pollen season* is defined as follows:

Start of season	First 3 consecutive days at pollen count >10 grains/cm ³
End of season	First 3 consecutive days at pollen count < 10 grains/cm ³
Start of peak season	First 3 consecutive days at pollen count >30 grains/cm ³
End of peak season	First 3 consecutive days at pollen count < 30 grains/cm ³

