7. ENDPOINT EVALUATION

7.1 Overview of Efficacy Analysis Methods

7.1.1 Assessment Time Windows

All study visits must occur within the time limits specified below:

Atopic

Phase I (all):

Screening Visit – Visit -1, from December 2013 to April 2014

Visit – 0a, after screening and before Visit 0b

Visit - 0b, from January 2014 to April 2014

Visit – 1, after Visit – 0b

Visit – 2, from February to May 2014

Visit – 3, from March to May 2014

Visit – 4, from April to June 2014

Visit – 5, from May to August 2014

Visit – 6, from July to October, 2014

Visit – 7, from January to April 2015

Phase II (active treatment group only)

Visit – 8, 24 months after start of treatment

Visit – 9, 36 months after start of treatment

Non-Atopic

Screening Visit – September 1st to November 30th, 2014

Visit – 1 coinciding with Visit 7 at 12 months of treatment of the atopic participants

Unscheduled visits may also occur throughout the study.

The pollen season will be defined as in the protocol. Pollen counts will be quantitated retrospectively for the purposes of analysis. *Pollen season* is defined as follows:

Start of season	First 3 consecutive days at pollen count >10 grains/cm ³
End of season	First 3 consecutive days at pollen count < 10 grains/cm ³
Start of peak season	First 3 consecutive days at pollen count >30 grains/cm ³
End of peak season	First 3 consecutive days at pollen count < 30 grains/cm ³

A variable for the pollen season and peak pollen season (0 = no pollen season, 1 = pollen season, 2 = peak pollen season) will be created by the AIT team indicating when the season started and finished.

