7.3.1 Exploratory Endpoints

The endpoints listed below will compare the following groups using the same statistical methodology as described for the primary endpoint.

- SLIT versus SLIT Placebo

1. Symptoms and medication scores (AUC) scores (Appendix 5 of the protocol) will be self-assessed weekly during the pollen season from May 2014 until end of July 2014 by the atopic participants. The symptom score will encompass nose and eye symptoms recorded on a scale from 0 to 3 (with a score of 0 indicating no symptoms, 1, 2 and 3 indicating mild, moderate and severe symptoms respectively). The maximum score is therefore 18. All possible rescue medication will be provided to each participant before the Hayfever season in May. They will be asked to use the treatment on an as required basis only, starting with the antihistamines (tablets and/or eye drops) and if this does not suffice adding treatment with nasal spray. In case this still does not relieve their symptoms they will be advised to contact the trial team to start Prednisolone 30 mg 3-5 days. Medication use will be recorded in weekly questionnaires by participants and a medication score will be calculated: desloratadine, 5 mg, up to 1 tablet daily and/or olopatadine eye drops, 1.0 mg/mL, up to 1 drop per eye twice daily (1 point per day); fluticasone nasal spray, 50 mcg per spray, up to 2 sprays per nostril once daily (2 points per day); and prednisone, 5 mg per tablet, up to 6 tablets per day (3 points per day). The maximum daily medication score will therefore be 3. The maximum weekly score will be 21. 21 will be divided by 7 and multiplied by 6, which gives us a maximum score of 18, to allow a comparison between symptom and medication scores, since maximum scores for symptoms and medications are different in magnitude, as recommended by World Allergy Organization (WAO) guidelines. A combined symptom and medication score in accordance with WAO guidance on immunotherapy trials will then be calculated by dividing both scores by 6, summarize of the results and divide by 2. This will be performed by the AIT trial team and send on excel files to the Inform database. The mean composite score in each treatment group during the pollen season (beginning of May to end of July) and during the peak pollen season (approximately

mid-June, defined as the max 14 day rolling average pollen count during the season) will be compared.

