2. Mini Rhinoconjunctivitis Quality-of-Life Questionnaire (miniRQLQ) scores will be collected weekly during the pollen season (Appendix 3 of protocol). The mean composite score in each treatment group during the peak pollen season (beginning of May to end of July) will be compared. Furthermore the maximum RQLQ will be compared.
Mini RQLQ will also be recorded pre- and post-season. Adding the scores of the 14 questions to form a single score per measurement will form the score of the mini RQLQ. The Inform database team will perform this.
3. Symptoms and severity of symptoms after intake of the daily tablets will be recorded on a daily questionnaire (Appendix 9 of protocol), which the participants will fill out at home. The type of symptom (itchy mouth, swelling of the mouth or other) and the WAO Grade of the local symptoms will be calculated daily and active will be compared. The duration of the symptoms in days and the duration of symptoms in minutes will be specified, the AIT trial team according to the records assessed on the paper CRF on every visit will give this information.
4. Global Evaluation Score 3 (Visual Analogue Scale of overall Hayfever symptoms in the last week) (Appendix 4 of protocol) will be collected weekly during the pollen season. The mean composite score in each treatment group during the peak pollen season (beginning of May to end of July) will be compared. Furthermore the maximum Global Evaluation Score 3 will be compared between the placebo and the active treatment group.
5. The total nasal symptoms score (TNSS) measured at 0, 5, 15, 30 and 60 minutes (Early phase response (EPR)) following grass pollen nasal allergen challenge at baseline, at 6 and at 12 months (Appendix 6) will be assessed similar to the primary endpoint.

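### SAP 7.3.1 reports May–July means of the miniRQLQ and weekly VAS as peak-season results, although item 1 of the same section calls those dates the whole season

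*SAP*

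**What the plan says.** Three descriptions of the peak season stand side by side.

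- **14-day maximum.** For the symptom-medication score, SAP 7.3.1 item 1 compares means "during the pollen season (beginning of May to end of July) and during the peak pollen season". It places the peak near the middle of June, "defined as the max 14 day rolling average pollen count during the season". Protocol 6.8.3.2 item 1 uses the same 14-day peak.
- **Calendar window.** For the miniRQLQ (item 2) and Global Evaluation Score 3 (item 4), the mean "during the peak pollen season (beginning of May to end of July) will be compared". Both items also compare the maximum score.
- **Count threshold.** In SAP 7.1.1, repeating protocol 6.5.5, the peak starts at the "First 3 consecutive days at pollen count >30 grains/cm" and ends at the "First 3 consecutive days at pollen count < 30 grains/cm". The whole season ends at the "First 3 consecutive days at pollen count < 10 grains/cm". The SAP then gives the trial team this task: "A variable for the pollen season and peak pollen season (0 = no pollen season, 1 = pollen season, 2 = peak pollen season) will be created". No endpoint in SAP 7.3 or 7.3.1 says that it uses this variable.

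The questionnaires are weekly from the start of May to the end of July (protocol 6.5.14). Appendices 4 and 5 fix Wednesday as the day; Appendix 3 says only weekly. Protocol 6.8.3.2 item 3 plans miniRQLQ scores before, at the peak of and after the pollen season.

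**The concern.** Within one SAP section the same dates are the whole season for one questionnaire and the peak for two others. An analyst who follows items 2 and 4 exactly will produce a three-month mean and label it a peak result. A reader will then set it beside the symptom-medication peak, which covers a fortnight. The two answer different questions, and agreement or disagreement between them could come from the windows alone.

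The SAP also leaves the miniRQLQ without a true peak mean, although the protocol lists a peak assessment. If the treatment difference is larger when pollen is high, the three-month mean understates it.

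A separate weakness lies in the threshold rule. The season closes at the first three low days, with no condition that counts stay low afterwards.

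**Working it through.** The plan states no figure on this point, so there is none to reproduce. The check compares the windows, then asks how much the difference could matter.

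**1. Length of each window.** 1 May to 31 July 2014 is 31 + 30 + 31 = 92 days and contains 13 Wednesdays (7 May to 30 July). Any 14-day window contains exactly 2 Wednesdays. The miniRQLQ is assumed to follow the same weekly day.

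| Definition | Used for | Days | Weekly forms |
|---|---|---|---|
| May–July | miniRQLQ, weekly VAS (called peak); symptom-medication score (called season) | 92 | 13 |
| Maximum 14-day average | symptom-medication score (called peak) | 14 | 2 |
| Threshold of 30 | 0/1/2 variable only | depends on counts | depends on counts |

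The fortnight is 14/92 = 15% of the days and 2/13 = 15% of the forms.

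**2. Share of a peak difference that the 13-form mean keeps.** Let the group difference be 1 in the 2 peak weeks and *r* in the other 11, with all forms weighted equally. The share kept is (2 + 11*r*)/13. The documents give no value of *r*, so a range is assumed.

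| *r* | Share kept |
|---|---|
| 0 | 2/13 = 15% |
| 0.25 | 4.75/13 = 37% |
| 0.50 | 7.5/13 = 58% |
| 0.75 | 10.25/13 = 79% |
| 1 | 13/13 = 100% |

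**3. Precision.** With a common within-person correlation ρ between weekly forms, the variance of a mean of *k* forms is proportional to ρ + (1 − ρ)/*k*. The SD of a 2-form mean relative to a 13-form mean is then:

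- ρ = 0.3 (assumed): √(0.650/0.354) = 1.36
- ρ = 0.7 (assumed): √(0.850/0.723) = 1.08

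Multiplying by the share kept gives the standardised difference of the 13-form mean relative to the 2-form mean. It is 0.40 to 0.50 at *r* = 0.25, 0.63 to 0.78 at *r* = 0.50, 0.85 to 1.07 at *r* = 0.75, and 1.08 to 1.36 at *r* = 1. Either window can be the more sensitive one.

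**4. The end rule, taken literally.** The documents contain no pollen data. An illustrative curve was assumed: a smooth hump with its maximum of 100 on 15 June and a spread (SD) of 16 days.

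| Assumed counts | Threshold peak | Threshold season |
|---|---|---|
| No dip | 22 May to 10 July, 49 days | 12 May to 20 July, 69 days |
| Dip to 5 on 6–8 June | closes 6 June, 15 days | closes 6 June, 25 days |
| Dip to 20 on 6–8 June | closes 6 June, 15 days | unchanged, 69 days |

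In both dip cases the counts return and stay above 30 until 9 July. The May–July window remains 92 days and 13 forms throughout.

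**The case against.** The strongest reply is that the dates in items 2 and 4 are explicit and match the collection period, so *peak* is probably a slip for *pollen season*. Protocol 6.2.2 itself chooses a whole-season mean for the symptom-medication score. On that reading the label is wrong and the period is not. This is fair, and it is why the documents do not support saying that the scores are averaged over the wrong period. It does not remove the need for a correction: the label would still mislead, and the SAP would still have no peak mean for the miniRQLQ.

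The maximum-score comparisons in items 2 and 4 are a genuine mitigation. They capture each person's worst week without any season definition. They are not a mean over a common peak window, so they replace the missing summary only in part.

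A reader might infer that the end rule distorts the miniRQLQ and VAS results. It cannot, because those windows are calendar dates. A reader might also take 15% as the expected loss, but that figure requires no treatment difference at all outside the fortnight, which nothing in the documents supports. Finally, one might say that three definitions leave the window open to choice after the data are seen. The room for this is limited, since each questionnaire item carries its own stated window.

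**Conclusion.** The inconsistency is real and should be corrected. As written, items 2 and 4 give a 92-day, 13-form mean the name of a peak result, and that mean is not comparable with the 14-day, 2-form symptom-medication peak.

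The size of any dilution cannot be fixed from the documents. Between 37% and 79% of a peak difference is kept if the off-peak difference is 25% to 75% of it, and all of it if the difference is constant. Those figures rest on equally weighted weekly forms and an assumed ratio. After allowing for the extra noise of two forms, even the direction of the effect on power is open.

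The end rule is a separate and conditional weakness. It matters only if the 0/1/2 variable enters an analysis, and no listed endpoint is expressly tied to it.

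The consequence is limited. The endpoints are exploratory in the SAP, the windows are the same in both arms, and the primary endpoint, a nasal challenge at 12 months, uses no season definition.

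**What to change.** 1. In SAP 7.3.1 items 2 and 4, rename the May–July mean as the pollen-season mean. Add a separate peak mean on item 1's 14-day window, and keep the maximum-score comparisons.
2. State how a weekly form is assigned to the 14-day window: by completion date or by the week it recalls. The forms ask about the past week, so the two can differ.
3. In both protocol 6.5.5 and SAP 7.1.1, do one of two things. Either state that the 0/1/2 variable is descriptive only, or define the end as the first 3-day run below threshold after the 14-day peak window with no later 3-day run above threshold. Changing only the SAP would leave the protocol in conflict with it.

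The cost is a few lines of text in two documents, settled before unblinding. No new data are needed. The statistical price is that the added peak mean rests on about 2 forms per person, with an SD roughly 1.08 to 1.36 times that of the 13-form mean under the correlations assumed above. A missed form also weighs more. Reporting both means avoids having to choose between them.

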7.3.2 Mechanistic Assessments

The endpoints listed below will compare the following groups using the same statistical methodology as described for the primary endpoint.

- SLIT versus SLIT Placebo
- SLIT versus SLIT Placebo versus non-atopic controls

Grass pollen specific immunological markers in serum, nasal fluid and nasal brushings will be evaluated at baseline, after 1, 2, 3 months, during the peak pollen season (at 4 months) and after 12 months of treatment. Comparisons will be made between atopic active and placebo group and at the 12 months' time point also with the non-atopic participants. Biopsies will be performed at baseline, after 12 months, 24 months of treatment and after 12 months of withdrawal.

Blood samples:

Analysis will be performed on baseline, 1, 2 and 3 months, peak pollen season and 12 months of treatment samples.

1. Immunocap (Total IgE, sIgE, sIgG4)
2. FAB-Assay
3. Basophil Activation
4. ILC2
5. IL-10 (ELISA)

Nasal Fluid:

The following analysis will be performed on baseline, 1, 2 and 3 months, peak pollen season and 12 months of treatment sample.

1. FAB-Assay
2. ISAC

The following analysis will be performed on baseline and 12 months sample.

1. Chemokines
Tryptase (baseline, 5, 15, 30 and 60 minutes and at 8 hours)
ECP and Eotaxin
 2. Cytokines (Multiplex) (baseline, 1 and 8 hours)
- Hierarchy of testing: IL-4, IL-5, IL-9, IL-13 (Th2-cytokines), possibly IFN γ , IL-10, TGF β
Eotaxin, MDC, TARC, ECP (Th2-chemokines)

8. SAFETY EVALUATION

8.1 Overview of Safety Analysis Methods

All safety analyses will be carried out using the safety sample defined in Section 3. Missing safety information will not be imputed. Safety will be analyzed through the reporting of adverse events (AEs).

8.2 Adverse Events

Side effects to the treatment will be recorded daily according to the WAO guidelines. They will be recorded as an Adverse Event (AE) only when the severity of the symptoms has a > Grade 1 according to WAO guidelines.

All AEs will be classified using the National Cancer Institute's (NCI's) Common Toxicity Criteria for Adverse Events (CTCAE). This will be performed by the AIT study team. Each AE is entered on the case report form (CRF) once at the highest severity and the duration of the AE will be recorded. Also information about System Organ Class – Term and CTCAE Term – Term will be included.

CTCAE classification version 4.03: http://evs.nci.nih.gov/ftp1/CTCAE/CTCAE_4.03_2010-06-14_QuickReference_8.5x11.pdf will be used by the AIT team and send to the Inform database via excel files.

An overall summary table will be developed to report the number of events and the number and percentage of subjects having at least one event in the following categories:

- AEs
- AEs indicated as serious
- AEs that lead to study drug discontinuation
- AEs with an outcome of death
- AEs that were reported as being related to a study drug
- AEs reported by maximum severity

Exploratory analysis will be carried out for the different type of adverse events to compare the intervention with control group: frequency tables, bar graphs, summary statistics.

8.3 Deaths and Serious Adverse Events

Serious adverse events (SAEs) will be listed and summarized. Separate displays listing and summarizing death, including time to death and cause of death, will also be created.

[figure not shown]
9. OTHER ANALYSES

9.1 Use of Medications

Medications will be coded according to the British National Formulary (BNF) wherever possible. Medications reported on the CRF will be categorized for analysis as prior, concomitant, or after study treatment by comparing the medication start and stop dates with the first and last dose of study medication dates. Prior medications will have both the medication start and stop dates prior to the first dose of study medication date. After medications will have both the medication start and stop dates after the last dose of study medication date. All other medications will be classified as concomitant, indicating that use of the medication overlapped with use of the study medication by at least one day. Descriptive statistics will be performed indicating the number and percentage of subjects receiving prior, concomitant, and after medications.

10. APPENDICES

10.1 Study Flow Chart (Phase I)

10.2 Schedule of Events

10.2.1 Assessments (Phase I and Phase II)

	Visit →	Screening Atopic	Screening Non Atopic	Visit 0a Atopic	Visit 0b Atopic	Visit 1 Atopic	Visit 2 Atopic	Visit 3 Atopic	Visit 4 Atopic	Visit 5 Atopic	Visit 6 Atopic	Visit 7 Atopic	Visit 8 Atopic active treated	Visit 9 Atopic active treated
General Assessments														
Informed Consent	Y	X	X											
Eligibility for the study		X	X											
Demographics		X	X											
Allergy History		X	X											
Medical History		X	X											
Drug History		X	X											
Limited Physical Exam		X	X											
Vital Signs		X	X			X	X	X	X	X	X	X	X	X
Haematology		X	X											
IgE, sIgE		X	X											
Spirometry		X	X											
Smoking History		X	X											
Adverse Events		X	X	X	X	X	X	X	X	X	X	X	X	X
Concomitant Medications		X	X	X	X	X	X	X	X	X	X	X	X	X
Assessment of compliance		X	X	X	X	X	X	X	X	X	X	X	X	X
Randomisation						X								
Intervention														
Grazax vs Placebo						X	X	X	X	X	X	X	X	X
Clinical Assessments														
Intradermal Allergen Challenge (1 BU)						X						X	X	X
Skin Test		X	X											
Urine Pregnancy Test		X	X											
Clinical Outcomes														
Diary Cards														
Global Evaluation (GE) Score 1		X	X										X	X
Global Evaluation (GE) Score 2		X	X										X	X
Global Evaluation (GE) Score 3		X	X										X	X
Mini Rhinoconjunctivitis Quality of Life		X	X											
Questionnaire		X	X											
Symptom Score		X	X											
Medication Score		X	X											
Nasal Allerg Challenge		X	X									X	X	X
Mechanistic Laboratory Assessments														
Serum for antibody assays				X		X	X	X	X	X	X	X	X	X
Whole blood for basophil assays				X		X	X	X	X	X	X	X	X	X
Whole blood for LC2				X		X	X	X	X	X	X	X	X	X
Whole blood for T-regs				X		X	X	X	X	X	X	X	X	X
Biopsies					X								X	X
